4.4 Exploratory Efficacy analyses

If an effect of randomised treatment is seen on the primary endpoint, then exploratory analyses will be performed assessing correlations between changes in d-dimer and changes in PAR-1 expression. Regression models will also be used to assess the extent to which differences in changes in d-dimer between randomised treatments are attenuated through adjustment for PAR-1 expression.

These analyses will be on a subset of participants for whom PAR-1 expression data are available. It is accepted that this will result in lower power, and results will be interpreted cautiously.

5 EVALUATION OF SAFETY PARAMETERS

Evaluation of safety parameters in participants who receive at least one dose of study therapy and attend at least one visit post randomisation with no imputation for missing data.

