6.2.2 Safety analysis

The proportion of participants with all DAIDS (Division of AIDS) grade adverse events and DAIDS grade 3/4 adverse events (see Appendix 1) will be summarised by randomised treatment group, by severity and by relation to study drug for all subjects treated with study drug. Serious adverse events will be summarised for all enrolled subjects. The analysis of safety variables will be done according to a per protocol approach.

A particular focus of safety analyses will be bleeding events. These will be solicited adverse events, and classified according to Bleeding Academic Research Consortium (BARC) criteria¹⁶ (see Appendix 2) as BARC Type 1, 2, 3, 4 or 5 bleeding events. Bleeding events reported as unsolicited adverse events or serious adverse events will also be summarised. The proportions of patients with bleeding events will be compared between treatment arms using chi-square tests. If numbers of events are small, some bleeding events may be aggregated.

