9.2.3 Randomisation and Drug Supply

After completion of all randomisation study visit assessments the participant will be randomised online via the web based CRF. Eligibility must be confirmed and the participant will then be automatically randomised to commence either vorapaxar sulphate (2.5mg) or matching placebo once daily. A Participant Identification (PID) number will be provided.

The treatment assignment will be stratified according to clinical site.

The investigator should complete a prescription and the participant should fill the prescription that same day or the next. Therefore, the study drug should be commenced within 1 day of randomisation.

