9.3 Follow Up Visits

The scheduled date of study visits will be calculated from the date of randomisation (day 0, week 0). A schedule of the dates for study visits will be provided for each participant, once randomisation has been completed. Guidance for site staff will also be detailed in the MOOP.

The window period for each study visit is continuous so that all data collected may be used. The window period for: week 1 is between day 1 and day 13 from randomisation (inclusive); week 4, 8 and 12 visits in each treatment phase should be conducted 2 weeks before or after the scheduled visit date. Week 18 to be conducted no later than 2 weeks after the scheduled visit date.

9.3.1 Clinical assessments at weeks 1, 4, 8, 12, 18

- Targeted physical examination (symptom directed) [weeks 1, 4, 8, 12, 18]
- Symptoms reported by the subject or symptoms identified after examination will be reviewed by the clinician at each visit and recorded on the CRFs as adverse events [weeks 1, 4, 8, 12, 18]
- Updated medical history including changes or additions to diagnoses, diseases, or any change in antiretroviral drugs, prescribed concomitant medications [weeks 1, 4, 8, 12, 18]
- Sitting blood pressure [weeks 1, 4, 8, 12, 18]
- Weight [week 18 only]
- Dispense study medication [weeks 4 and 8 only]

9.3.2 Laboratory assessments at weeks 1, 4, 8, 12, 18

- If the participant is female and is of child bearing potential, she must have a urine or blood sample pregnancy test [weeks 4, 8, 12, 18]
- Haematology: full blood count (haemoglobin, white cells, neutrophils, lymphocytes, platelets) [weeks 1, 4, 8, 12, 18]
- Blood sample for haemoglobin measurement to be taken if the participant experiences a clinically significant bleeding event (clinical judgement to be used)
- Plasma HIV-RNA levels [weeks 1, 4, 8, 12, 18]
- Immunology: CD4 and CD8 (% and absolute) [weeks 1, 4, 8, 12, 18]
- Serum chemistries and liver function tests: electrolytes (sodium, potassium, bicarbonate, chloride, phosphate), urea, creatinine and LFTs (ALT and AST only) [weeks 12 and 18 only]
- PAR-1 (to be analysed in a subset of participants from selected sites with capacity to perform this assay in real time) [weeks 1, 4, 12, 18]
- Plasma storage for central laboratory testing of d-dimer, Hs-CRP, IL-6 [weeks 1, 4, 8, 12, 18]
- Plasma, PBMC and serum storage for possible exploratory analysis of T cell activation, NK cell function and ADCC antibody [weeks 1, 4, 8, 12, 18]

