9.5 Withdrawal of study participants

In general terms, all randomised study participants should remain in follow-up for the duration of the study, regardless of whether or not they continue to take randomly assigned therapy. All study participants should continue to attend all study visits and complete all study-mandated assessments as per protocol. No participants will be replaced if there is a withdrawal.

The reasons for premature study discontinuation and withdrawal of participants from the study include the following criteria:

- Termination of the study by the Protocol Steering Committee
- Withdrawal of consent - participants may revoke consent for follow-up without jeopardising their relationship with either their doctor or the Sponsor. If a participant revokes consent then, if possible, all assessments scheduled for the final visit should be completed. The date of the withdrawal of consent must be documented in the participant’s medical notes. See MOOP for more details.

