10.3.2.5 BARC Type 5 Bleeding

If any participant suffers a fatal bleed the blind for that participant will be broken. If the participant was taking vorapaxar at the time of the event, the trial will be temporarily stopped whilst the Data Safety Monitoring Board (DSMB) reviews the event in light of other clinical safety information for the study. Please see section 18.0 for details on DSMB.

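### SAP 5 limits every safety table to dosed participants who attended a visit, a narrower set than protocol 6.2.2 names for AEs and SAEs; few or none are likely to be affected

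*SAP*

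**What the plan says.** SAP 5 opens with one population for the whole safety evaluation: "participants who receive at least one dose of study therapy and attend at least one visit post randomisation". It adds that missing data will not be imputed. SAP 5.2 (bleeding, SAEs, AEs, laboratory events) and SAP 5.3 (serious non-AIDS events, AIDS, pregnancies, deaths) name no other set, so the opening sentence governs them all. SAP 1.3 assigns all endpoints to an mITT set with much the same two conditions: some study drug and some follow-up. Protocol 5.5 lists the safety measures among the endpoints, so SAP 1.3 reaches them too.

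Protocol 6.2.2 makes three statements about who is counted:

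- AEs are tabulated by arm, by grade, and then "by relation to study drug for all subjects treated with study drug", with no visit requirement.
- For SAEs the set is wider still: "Serious adverse events will be summarised for all enrolled subjects", so neither a dose nor a visit is required.
- A closing sentence cuts across both: "The analysis of safety variables will be done according to a per protocol approach". The term is not defined there.

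On timing, protocol 9.2.3 says "the study drug should be commenced within 1 day of randomisation", and protocol 9.3 places the week 1 visit between days 1 and 13. Protocol 11.2.1 collects SAEs from consent and requires prompt reporting that does not wait for a visit. Protocol 9.5 says "all randomised study participants should remain in follow-up for the duration of the study", on or off drug.

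**The concern.** Membership of a safety set should not depend on what happens after dosing. Attending a visit is such an occurrence, and a fatal or disabling event is one reason not to attend. A participant who takes study drug, has an early major bleed and never attends would be removed by a stated rule, even though the event is already in the SAE records. Protocol 6.2.2 makes bleeding a particular focus of the safety analysis, so this is the kind of event that the final tables most need to show.

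What is at stake is limited to the counts, denominators and comparisons in the final safety tables, and to a SAP population that does not match the protocol's.

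**Working it through.** **1. The sets side by side**

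| Outcome | Protocol 6.2.2 | SAP 5 | Added by the SAP |
|---|---|---|---|
| AEs, including bleeding | all treated | dosed and attended a visit | visit condition |
| SAEs | all enrolled | dosed and attended a visit | dose and visit conditions |
| Deaths | no set of their own (a death is an SAE under protocol 11.2) | dosed and attended a visit | as for SAEs |

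**2. Who is excluded**

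Any later visit satisfies SAP 5. Someone with an event on day 5 who misses week 1 but attends week 4 is counted. The excluded group is therefore dosed participants with no visit at all up to week 18, plus, for SAEs, anyone randomised but never dosed.

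**3. How many**

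The documents give no count. With 60 randomised (protocol 6.0) and an assumed exclusion rate r, the expected number is 60r and the chance of at least one is 1 − (1 − r)^60:

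| Assumed r | Expected excluded | P(at least one) |
|---|---|---|
| 0.5% | 0.3 | 0.26 |
| 1% | 0.6 | 0.45 |
| 2% | 1.2 | 0.70 |
| 5% | 3.0 | 0.95 |

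SAP 1.3 calls follow-up excellent, which points to the low end or to zero.

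**4. Effect on a rate**

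Assume 30 per arm (60 randomised 1:1) and one excluded participant who had an event. If x participants in that arm had events, the rate changes from x/30 to (x − 1)/29, a fall of x/30 − (x − 1)/29 = (30 − x)/870.

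| x | All dosed | After exclusion | Fall (points) |
|---|---|---|---|
| 1 | 1/30 = 3.3% | 0/29 = 0.0% | 3.3 |
| 2 | 2/30 = 6.7% | 1/29 = 3.4% | 3.2 |
| 3 | 3/30 = 10.0% | 2/29 = 6.9% | 3.1 |
| 6 | 6/30 = 20.0% | 5/29 = 17.2% | 2.8 |

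If the excluded participant had no event, the rate rises by x/29 − x/30 = x/870, which is 0.1 to 0.7 points for x = 1 to 6.

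**5. Effect on the test**

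The plan gives no expected safety event rates, so these tables are illustrations. Two-sided Fisher p:

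| All dosed | p | One participant with an event excluded | p |
|---|---|---|---|
| 6/30 vs 1/30 | 0.103 | lower arm: 6/30 vs 0/29 | 0.024 |
| 3/30 vs 1/30 | 0.612 | lower arm: 3/30 vs 0/29 | 0.237 |
| 3/30 vs 1/30 | 0.612 | higher arm: 2/29 vs 1/30 | 0.612 |
| 6/30 vs 0/30 | 0.024 | higher arm: 5/29 vs 0/30 | 0.024 |

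So the result depends on which arm loses the participant. Uncorrected chi-square, the test named in protocol 6.2.2, also moves when the higher arm loses one: 6/30 vs 1/30 goes from 0.044 to 0.077 (5/29 vs 1/30), and 6/30 vs 0/30 goes from 0.010 to 0.017 (5/29 vs 0/30). These cells are sparse, so Fisher may be preferred.

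No sample size or power figure in the plan depends on this point.

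**The case against.** **Attendance has a purpose.** AEs are recorded at visits (protocol 11.1), bleeding events are solicited (protocol 6.2.2), and laboratory events need a follow-up sample. Someone who never attends has unknown status for these outcomes, and putting that person in the denominator treats unknown as event-free. This stands for laboratory events. It does not stand for SAEs and deaths, which are reported outside visits, nor for a bleed that comes to light as an SAE. For other bleeding and non-serious AEs the dilution from one such person is 0.1 to 0.7 points, and reporting how many dosed participants had no visit makes it visible.

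**The protocol is not consistent either.** If its per-protocol sentence governed and meant on-treatment events only, SAP 5 would be broader than the protocol in that respect. That is fair, and it is why all the statements need reconciling. The phrase contains no attendance test, however, so it does not support the condition in SAP 5.

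**Stronger readings that a reader might infer.**

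- *That early deaths or bleeds have been hidden.* No excluded participant is documented.
- *That every event before the week 1 visit is lost.* Any later visit restores the participant.
- *That off-drug events will be dropped from safety.* This needs the per-protocol phrase to mean censoring when drug stops. SAP 1.3 keeps data regardless of drug status, and mentions such censoring only as a sensitivity analysis not thought necessary.
- *That safety surveillance is weakened.* SAE reporting is unchanged. Protocol 10.3.2.5 says "If any participant suffers a fatal bleed the blind for that participant will be broken", with review by the Data Safety Monitoring Board if the participant was taking vorapaxar.

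**The word enrolled is undefined.** Protocol 8.2 uses it in a way that suggests randomised. If it meant consented, about 60 screen failures (120 screened less 60 randomised, protocol 6.0) would also fall under the SAE sentence.

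**Conclusion.** The mismatch is real and minor. SAP 5 adds a post-treatment attendance condition that neither the AE nor the SAE sentence of protocol 6.2.2 contains, gives no reason for it, and applies it to deaths. That conclusion rests on the text alone and is firm.

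The size is conditional. If nobody is excluded, which the SAP's comment on follow-up makes likely but no count confirms, no result changes. With 30 per arm and one excluded participant who had an event, the arm's rate falls by 2.8 to 3.3 points for 1 to 6 participants with events. The comparison may stay the same or change materially, depending on the arm. It would be wrong to assume that the test is unaffected.

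**What to change.** In SAP 5:

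- Define the safety set as all randomised participants who took at least one dose, with no attendance or follow-up condition. Use it for AEs, bleeding events, SAEs and deaths to week 18, whether or not drug was stopped.
- List SAEs and deaths in randomised but undosed participants separately, and state that enrolled is taken to mean randomised.
- For laboratory events, use participants with a post-baseline sample as the denominator.
- Report by arm how many dosed participants attended no visit.

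In SAP 1.3, state that the mITT set applies to efficacy endpoints only. Otherwise it would still contradict the revised SAP 5.

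The per-protocol sentence in protocol 6.2.2 must be reconciled with the two sets stated just before it and with SAP 5. At the least, the SAP should record which statement governs and how the phrase is read.

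The cost is a few SAP sentences and no new data. The SAP edits need no change to protocol text. Rewording protocol 6.2.2 itself would need ethics approval of an amendment first, under protocol 15.2.

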5.2 Adverse Events

Bleeding adverse events

Total number of participants with Type 1, 2, 3, 4 or 5 bleeding episodes using BARC criteria. Bleeding episodes will be summarised by type and randomised treatment.

Serious Adverse Events

Total number of participants with any Serious Adverse Event (SAE) and the cumulative incidence of SAEs. SAEs will be summarised by randomised treatment and relationship to study drug.

Adverse events

Total number of participants with any Adverse event (AE) and the cumulative incidence of AEs. All AEs, and grade 3 or 4 AEs, will be summarised by MedDRA group term, relationship to study drug and randomised treatment.

Laboratory adverse events

Total number of participants with laboratory or biochemical adverse events, according to DAIDS criteria, in particular renal function measured by the CKD-EPI estimate of creatinine clearance. Laboratory AEs will be summarised by grade and randomised treatment.

Statistical analysis of adverse event data

The proportion of patients with adverse events will be compared between randomised treatments using chi-square tests, Fisher's exact test or similar as appropriate to the data. Differences in proportions of patients with events by randomised treatments will be summarised as 95% confidence intervals.

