5.5 Secondary endpoints

Secondary endpoints to be measured during the two treatment phases will include, but not be limited to the following:

Virologic measures of interest

- Proportion of participants in each treatment group with plasma HIV-1 RNA <50 copies/mL at week 12 and week 18

Immunologic measures of interest

- Differences between treatment groups in mean change from baseline in CD4+ cell counts at week 12
- Differences between treatment groups in mean change from baseline in CD4+ cell counts at week 18
- Differences between treatment groups in mean change from baseline in CD8+ cell counts at week 12
- Differences between treatment groups in mean change from baseline in CD8+ cell counts at week 18

Activation/Coagulation measures of interest

- Percentage of patients in each treatment group with d-dimer <165ng/mL (0.165mg/L) at week 8 and week 12
- Percentage of patients in each treatment group with d-dimer >165ng/mL (0.165mg/L) at week 18
- Differences between treatment groups in mean change from baseline log₁₀ d-dimer at week 18
- Differences between treatment groups in mean change from baseline log₁₀ hs-CRP at week 8 and week 12
- Differences between treatment groups in mean change from baseline log₁₀ hs-CRP at week 18
- Differences between treatment groups in mean change from baseline log₁₀ IL-6 at week 8 and week 12
- Differences between treatment groups in mean change from baseline log₁₀ IL-6 at week 18

Safety endpoints

- Total number of participants in each treatment group with Type 1, 2, 3, 4 or 5 bleeding episodes (using BARC¹⁶ criteria – see Appendix 2)
- Total number of participants in each treatment group with any Serious Adverse Event (SAE) and the cumulative incidence of SAEs.
- Total number of participants in each treatment group with any Adverse event (AE) and the cumulative incidence of AEs
- Changes from baseline in selected serum biochemical parameters, including changes in renal function measured by the CKD-EPI estimate of creatinine clearance

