10.3 Protocol-specific toxicity management guidelines

10.3.1 Vorapaxar Side Effect Profile

The most common AEs associated with the use of vorapaxar sulphate (2.5mg) given once daily in patients with a history of cardiovascular disease are bleeding (including intracerebral bleeding), anaemia, depression and rash, retinal disorder and diplopia/oculomotor disturbance. The most clinically relevant are summarised below.

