11.0 Adverse Event Recording & Reporting

11.1 Adverse Events

The definition of an adverse event is any untoward medical occurrence in a participant administered with a pharmaceutical product which does not necessarily have a causal relationship with the product. Where adverse events are related to the drug, they may be referred to as Adverse Drug Reactions.

Adverse events and adverse drug reactions may occur in the course of this study and within the specified follow-up period. These events may also occur in screened participants during the screening period prior to

randomisation as a result of protocol-specified interventions. All such events will be recorded at each study visit on the adverse event case report form.

In this study we will be collecting all grade (grade 1-4) clinical adverse events. As a general rule, isolated laboratory abnormalities in the absence of clinical symptoms and/or signs should not be captured as adverse events. If the laboratory event becomes clinically significant, then the resulting clinical event should be reported as an adverse event (e.g. low haemoglobin should be reported as anaemia).

Pre-existing conditions or diseases that occur during the study (e.g. seasonal allergies, asthma or recurrent headaches) should not be considered as adverse events unless they change in frequency or severity. In this study we will be collecting all grade (grade 1-4) clinical adverse events. If known, the diagnosis of the underlying illness or disorder should be recorded, rather than its individual symptoms.

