Potassium, Low (mEq/L; mmol/L)	3.0 to < 3.4 3.0 to < 3.4	2.5 to < 3.0 2.5 to < 3.0	2.0 to < 2.5 2.0 to < 2.5	< 2.0 < 2.0
Sodium, High (mEq/L; mmol/L)	146 to < 150 146 to < 150	150 to < 154 150 to < 154	154 to < 160 154 to < 160	≥ 160 ≥ 160
Sodium, Low (mEq/L; mmol/L)	130 to < 135 130 to < 135	125 to < 130 125 to < 135	121 to < 125 121 to < 125	≤ 120 ≤ 120
Uric Acid, High (mg/dL; mmol/L)	7.5 to < 10.0 0.45 to < 0.59	10.0 to < 12.0 0.59 to < 0.71	12.0 to < 15.0 0.71 to < 0.89	≥ 15.0 ≥ 0.89

¹⁶ To convert a magnesium value from mg/dL to mmol/L, laboratories should multiply by 0.4114.

Hematology

PARAMETER	GRADE 1 MILD	GRADE 2 MODERATE	GRADE 3 SEVERE	GRADE 4 POTENTIALLY LIFE- THREATENING
Absolute CD4+ Count, Low (cell/mm ³ ; cells/L) > 5 years of age (not HIV infected)	300 to < 400 300 to < 400	200 to < 300 200 to < 300	100 to < 200 100 to < 200	< 100 < 100
Absolute Lymphocyte Count, Low (cell/mm ³ ; cells/L) > 5 years of age (not HIV infected)	600 to < 650 0.600 x 10 ⁹ to < 0.650 x 10 ⁹	500 to < 600 0.500 x 10 ⁹ to < 0.600 x 10 ⁹	350 to < 500 0.350 x 10 ⁹ to < 0.500 x 10 ⁹	< 350 < 0.350 x 10 ⁹
Absolute Neutrophil Count (ANC), Low (cells/mm ³ ; cells/L) > 7 days of age	800 to 1,000 0.800 x 10 ⁹ to 1.000 x 10 ⁹	600 to 799 0.600 x 10 ⁹ to 0.799 x 10 ⁹	400 to 599 0.400 x 10 ⁹ to 0.599 x 10 ⁹	< 400 < 0.400 x 10 ⁹
2 to 7 days of age	1,250 to 1,500 1.250 x 10 ⁹ to 1.500 x 10 ⁹	1,000 to 1,249 1.000 x 10 ⁹ to 1.249 x 10 ⁹	750 to 999 0.750 x 10 ⁹ to 0.999 x 10 ⁹	< 750 < 0.750 x 10 ⁹
≤ 1 day of age	4,000 to 5,000 4.000 x 10 ⁹ to 5.000 x 10 ⁹	3,000 to 3,999 3.000 x 10 ⁹ to 3.999 x 10 ⁹	1,500 to 2,999 1.500 x 10 ⁹ to 2.999 x 10 ⁹	< 1,500 < 1.500 x 10 ⁹
Fibrinogen, Decreased (mg/dL; g/L)	100 to < 200 1.00 to < 2.00 OR 0.75 to < 1.00 x LLN	75 to < 100 0.75 to < 1.00 OR ≥ 0.50 to < 0.75 x LLN	50 to < 75 0.50 to < 0.75 OR 0.25 to < 0.50 x LLN	< 50 < 0.50 OR < 0.25 x LLN OR Associated with gross bleeding
Hemoglobin¹⁷, Low (g/dL; mmol/L) ¹⁸ ≥ 13 years of age (male only)	10.0 to 10.9 6.19 to 6.76	9.0 to < 10.0 5.57 to < 6.19	7.0 to < 9.0 4.34 to < 5.57	< 7.0 < 4.34
≥ 13 years of age (female only)	9.5 to 10.4 5.88 to 6.48	8.5 to < 9.5 5.25 to < 5.88	6.5 to < 8.5 4.03 to < 5.25	< 6.5 < 4.03

¹⁷ Male and female sex are defined as sex at birth.

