Appendix 2: Bleeding Academic Research Consortium (BARC) Definitions for Bleeding Events

Type 0	no bleeding
Type 1	bleeding that is not actionable and does not cause the patient to seek unscheduled performance of studies, hospitalization, or treatment by a healthcare professional; may include episodes leading to self-discontinuation of medical therapy by the patient without consulting a healthcare professional
Type 2	any overt, actionable sign of haemorrhage (eg, more bleeding than would be expected for a clinical circumstance, including bleeding found by imaging alone) that does not fit the criteria for type 3, 4, or 5 but does meet at least one of the following criteria: (1) requiring nonsurgical, medical intervention by a healthcare professional, (2) leading to hospitalization or increased level of care, or (3) prompting evaluation
Type 3	
Type 3a
 
 Overt bleeding plus hemoglobin drop of 3 to <5 g/dL* (provided hemoglobin drop is related to bleed) Any transfusion with overt bleeding 
Type 3b
 
 Overt bleeding plus hemoglobin drop ≥ 5 g/dL* (provided hemoglobin drop is related to bleed) Cardiac tamponade Bleeding requiring surgical intervention for control (excluding dental/nasal/skin/hemorrhoid) Bleeding requiring intravenous vasoactive agents 
Type 3c
 
 Intracranial hemorrhage (does not include microbleeds or hemorrhagic transformation, does include intraspinal) Subcategories confirmed by autopsy or imaging or lumbar puncture Intraocular bleed compromising vision

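### Haemoglobin is measured at every visit, but the only direct analysis of its values is a count of DAIDS grades, which cannot see a fall that ends above the grade 1 cut-off

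*SAP*

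**What the plan says.** Protocol 10.3.1 says that the most common adverse events with vorapaxar "are bleeding (including intracerebral bleeding), anaemia, depression and rash", among others. Table 1 in Protocol 10.3.3 gives anaemia in 5% of vorapaxar and 4% of placebo recipients, pooled over two cardiovascular trials.

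Haemoglobin is taken at screening and week 0 (Protocol 9.1.2 and 9.2.2) and at each later visit (Protocol 9.3.2): "Haematology: full blood count (haemoglobin, white cells, neutrophils, lymphocytes, platelets) [weeks 1, 4, 8, 12, 18".

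Three places bear on how the values are analysed:

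- **SAP 5.2, laboratory adverse events.** The measure is "Total number of participants with laboratory or biochemical adverse events, according to DAIDS criteria", and "Laboratory AEs will be summarised by grade and randomised treatment". Renal function is the only item singled out.
- **Protocol 5.5, safety endpoints.** The change-from-baseline endpoint is "Changes from baseline in selected serum biochemical parameters", including renal function. Haematology is not named.
- **SAP 4.3.** Summaries by visit and repeated-measures comparisons are specified for efficacy endpoints only.

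Haemoglobin also enters two event counts indirectly. BARC type 3a (Protocol Appendix 2) includes "Overt bleeding plus hemoglobin drop of 3 to <5 g/dL", and type 3b covers larger falls. Protocol 11.1 says that, by default, "isolated laboratory abnormalities in the absence of clinical symptoms and/or signs should not be captured as adverse events", but a laboratory change that becomes clinically significant is reported as the clinical event, with anaemia as its example.

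**The concern.** Haemoglobin is a repeated, objective measure related to two named risks of the drug, yet the plan reduces it to whether a participant crosses a fixed line. The DAIDS table (Protocol Appendix 1, haematology, low haemoglobin) sets grade 1 for men aged 13 and over at "10.0 to 10.9 6.19 to 6.76" (g/dL, then mmol/L). For women it is 9.5 to 10.4 g/dL. The general instructions to that table leave values between the lower limit of normal and grade 1 ungraded. A man who goes from 14.5 to 11.5 g/dL has lost 3 g/dL, the size used in BARC type 3a, and contributes nothing to the laboratory count.

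With 60 participants, and people at high risk of bleeding excluded (Protocol 10.3.2), clinical bleeds may be few. Protocol 6.1 ties the results to whether larger studies in people with HIV are justified. A near-empty grade table could then be read as reassurance that it cannot give.

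**Working it through.** **1. Plan's own figure.** The documents give no power or precision figure for haemoglobin. The power formula used below does reproduce the d-dimer sample size in Protocol 6.1. The SD of the mean of two visits is 0.4 × √((1 + 0.5)/2) = 0.346. For a difference of 0.26 at 80% power, n = 27.9, so 28 per arm. For 0.30 at 90% power, n = 28.02, and power at 28 per arm is 89.98%. Both agree with the protocol.

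**2. Largest fall that stays ungraded.** This follows from the documents alone: week-0 value minus the lowest ungraded value (11.0 g/dL in men, 10.5 in women).

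| Week-0 value (g/dL) | Men | Women |
|---|---|---|
| 12.0 | 1.0 | 1.5 |
| 13.0 | 2.0 | 2.5 |
| 13.5 | 2.5 | 3.0 |
| 14.0 | 3.0 | 3.5 |
| 14.5 | 3.5 | 4.0 |

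A 3 g/dL fall is therefore ungraded from 14.0 (men) or 13.5 (women) upward. A 2 g/dL fall is ungraded from 13.0 (men) or 12.5 (women) upward.

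**3. Share of participants affected.** This needs a baseline distribution and a sex mix, which the documents do not give. Assume normal baselines cut at the entry floor of 10.0 g/dL, with SD 1.0 to 1.5, means of 13.5 to 15.0 in men and 12.5 to 13.5 in women, and 60% to 95% men. The share in whom a 3 g/dL fall is ungraded then runs from 26% to 84%. For a 2 g/dL fall it is 65% to 98% of men and 52% to 85% of women.

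**4. Power for a 0.5 g/dL mean shift.** Assume 30 per arm, two-sided 0.05, SD of change s = 0.6, 0.8 or 1.0 g/dL, and correlation 0.5 between visits.

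- *Mean change over weeks 4, 8 and 12.* The SD of the three-visit mean is s × √((1 + 2 × 0.5)/3) = 0.816s, and the standard error is 0.816s × √(2/30). For s = 0.8 this is 0.169, and power = Φ(0.5/0.169 − 1.96) = 84%. For s = 0.6 it is 98% and for s = 1.0 it is 66%. Simulation of the baseline-adjusted analysis gives 63% to 98% over the same range.
- *Mean change at a single visit.* For s = 0.8, power is 68%.
- *Any DAIDS grade, men.* With baseline SD 1.2 and s = 0.8, the SD of a follow-up value is √(1.2² + 0.8²) = 1.44. For a baseline mean of 14.5 the graded share is 0.7% v 1.7%, with 5.5% power. For a mean of 13.5 it is 3.9% v 7.8%, with 9.4% power.
- *Newly graded participants, Fisher's exact test, by simulation.* Power is 0.3% or less with means of 14.5 in men and 13.0 in women and 90% men. It is 3% to 6% with 13.5, 12.5 and 70% men.

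**5. Power at a shift nearer the documents' own figure.** Treat anaemia as a fixed cut-off on a normal scale. Then 5% v 4% implies a shift of (1.751 − 1.645) × SD = 0.106 × SD. For a haemoglobin SD of 1.0 to 1.5 g/dL this is 0.11 to 0.16 g/dL. By the step 4 formula (both tails), power on three-visit mean change is 8% to 24%. For shifts of 0.1 to 0.2 it is 8% to 35%.

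**6. Precision.** The 95% half-width for the week-12 difference is 2.002 × s × √(2/30), which is 0.31, 0.41 or 0.52 g/dL for s = 0.6, 0.8 or 1.0.

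**The case against.** The best defence is that the values do more work than SAP 5.2 suggests. A fall of 3 g/dL or more with overt bleeding becomes a BARC type 3 event. A sample is taken at a suspected clinically significant bleed in order to classify it (Protocol 10.3.2). Clinically significant low haemoglobin is reported as anaemia and compared between arms with other AEs. BARC type 2 includes bleeding found by imaging alone and bleeding that prompts evaluation, bleeding is solicited (Protocol 6.2.2), and sites see haematology results in real time. All of this stands. A reader might infer that haemoglobin gets no other analysis, or that slow or occult loss is seen nowhere. The documents do not support either reading. The gap is a fall judged not clinically significant, with no bleeding identified, that ends above the DAIDS cut-off.

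The second defence is that the size of the problem rests on assumptions. This also stands. The documents do not show that 3 g/dL falls go ungraded in most participants, because the answer depends on baseline values that they do not give. Nor do they suggest a mean fall of 0.5 g/dL. Their only figure is 5% v 4% anaemia, from cardiovascular trials. In one of these, 88% took aspirin and 78% a thienopyridine, whereas current aspirin, P2Y12 and anticoagulant users are excluded here. A large contrast in power is a property of the assumed shift, not a finding about this trial.

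Third, the list of secondary endpoints in Protocol 5.5, which contains the safety endpoints, is explicitly open-ended, so a haemoglobin table is not ruled out and no stated endpoint goes unanalysed without one. That is correct, but an analysis added after unblinding carries less weight than one specified beforehand.

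**Conclusion.** The point holds as an inexpensive improvement, not as a defect that invalidates the safety analysis. From the documents alone, the values get no summary by visit and no change from baseline, and the grade count is blind to falls of 2 to 3 g/dL or more in participants who start above the values in the table.

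Baseline-adjusted mean change was more sensitive than the grade count in every scenario compared. For a 0.5 g/dL shift it has roughly 63% to 98% power, against under 10%, if the SD of change is 0.6 to 1.0 g/dL, the correlation between visits is 0.5 and there are 30 per arm. For a shift of 0.1 to 0.2 g/dL, nearer to what the anaemia figures suggest, neither analysis would detect it reliably. The gain is then an estimate whose interval, about ±0.3 to ±0.5 g/dL at week 12, shows what the trial can and cannot exclude.

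A reader might go further and say that the plan would give a false all-clear. The documents do not show that vorapaxar lowers mean haemoglobin by any given amount in this population, so the supportable statement is that a moderate mean fall would probably be missed by the grade count.

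**What to change.** Add two items to SAP 5.2, in the safety population of SAP section 5:

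1. Haemoglobin change from week 0, summarised by visit and arm. Give the between-arm difference with 95% CI over weeks 4, 8 and 12, and separately at week 18, from the repeated-measures method of SAP 4.3 with week-0 haemoglobin as covariate.
2. The number of participants per arm whose largest post-dose fall from week 0 is at least 2 g/dL, and at least 3 g/dL, whether or not bleeding was reported. State whether unscheduled samples taken at suspected bleeds count.

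Keep the DAIDS table, and present the new results as safety estimates rather than tests.

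The cost is a few lines of SAP text, one model and one table on data already collected. No samples, visits or staff are added. The drawback is one more safety comparison, to be read through its interval. The change concerns analysis only and does not touch patient management. Restoring the biochemistry change-from-baseline endpoint would not serve instead, because it does not reach haemoglobin. Counting only new grades would not either, because it cannot show a fall that lies wholly in the ungraded range.
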